### Control Variables

The control variables will be measured at baseline and will provide added control for pre-intervention influences so that the effect of trial arms will be rigorously isolated over and above other factors. The cognitive variables (working memory, cognitive status), independence in ADL's, and mobility aids will also be measured at each time period (1,3, 6, and 12 months) to account for changes over time which may affect wayfinding performance.

- **Cognitive Status.** The Montreal Cognitive Assessment (MoCA) is a 10 minute, 30 point instrument that tests short term memory recall, visuospatial abilities, executive functioning, attention, concentration and working memory, language, and orientation. The internal consistency (Cronbach's alpha) reported as .83. The MoCA has reported sensitivity for identifying mild cognitive impairment at 90% and AD 100% which is much more sensitive than the MMSE. In addition, the Mini Mental Status Examination (MMSE) will be administered. The MMSE is an 11-item (30 point) screening tool that assesses orientation, attention, immediate and short-term recall, language, and spatial ability. A cut score of up to 27 has been shown to have sensitivity of .89 and specificity of 0.91 in identifying those with dementia. The MMSE will be used along with the MoCA to describe the overall cognition of the subjects.
- **Working Memory.** The Digit Span tests will be used to assess working memory and attention, as these factors have been shown to impact spatial learning ability. Subjects are asked to repeat an increasingly larger series of numbers in the Digit Span Forwards test (DSF). In the Digit Span Backwards (DSB) test, subjects repeat the numbers in reverse order. Normal scores for the DSF test are > 5 and > 4 for DSB. Test-retest reliability of the digit span tests range from.
- **Age.** Age will be included on the demographic questionnaire and reported in years.
- **Education:** This will be included on the demographic questionnaire and recorded as years of school completed. Education is important to control for as it is often associated with cognitive performance.
- **Sex.** Sex will be a dichotomous variable on the demographic questionnaire with 2 responses: male or female. The purpose of including this variable is that the male sex has frequently been shown to have an advantage in wayfinding tasks. In addition, males have been shown to use different wayfinding strategies than females; and may be less reliant on cues.

- Mobility aids used: This will be measured by asking the subjects to identify the mobility aids they use in everyday activities, including: 1) No aids 2) Cane 3) Walker 4) Wheelchair and 5) Scooter and 6) Other.
- Activities of daily living (ADL) ability. The Katz Index of Independence in Activities of Daily Living 56 scale will be used to measure the ability of the subject to perform daily functions, such as bathing, eating, dressing, and toileting. The subject is rated as having total independence (1 point) or needing help (0 points) on six ADL's for a maximum score of 6. High scores indicate more independence in function. This scale has been used extensively for measurement of functional ability in older adults and has been shown to have predictive validity 57. This scale will provide information about differences in level of dependence of the subjects which may be related to their wayfinding performance.
- Diagnoses. To determine any medical diagnoses that could impact wayfinding ability, including neurological diseases such as stroke, Parkinson's disease, Alzheimer's disease, and others, the primary health care provider for each participant will be contacted (after permission/HIPAA release is obtained) and asked to send a list of all medical diagnoses.
- Reading ability: Subjects will have a brief reading test to determine their ability to read signage (different size fonts) and comprehend it. This test requires subjects to read prompts at various font sizes and perform the associated action (i.e. "Pat your head"). This data will be used to determine the subjects' ability to read and comprehend the signage40.

#### Feasibility Measures

Since this is a pilot RCT requested by PAR-16-365, Pilot Clinical Trials for the Spectrum of Alzheimer's Disease and Age Related Cognitive Decline, several measures of feasibility are included. Of primary concern is the tolerance of the testing by the subjects, acceptance of the cues by the residents within the communities; and the opinion of the usefulness of the cues by the LTC staff. The measures of feasibility are:

- The number of participants who could complete the entire study which will be obtained by the tracking study participation and attrition.
- Reason for attrition will be collected ongoing in the study by the data collectors.
- Resident acceptance of cues will be assessed using an anonymous questionnaire for all residents within the community at the completion of the study. Since a primary concern of many LTC communities is to provide a decorative and pleasing décor, it will be important to ascertain that the cues used within the care communities are acceptable. The survey will give important information about the preferences of the residents.
- Staff opinions of the utility of the cues will be assessed using focus groups and individual interviews. The staff within the community will be queried about their opinions about the usefulness of the cues for assisting residents in wayfinding; as well as their thoughts on the decorative element of the cues.

#### Study Outcomes (Dependent Variables)

Primary Outcome: Wayfinding Performance. Wayfinding is the ability of participants to find their way to key locations and back to the starting point (bedroom, dining area; and back to starting place).

Wayfinding performance will be measured at times 0, 1, 3, 6 and 12 months using the method of Brush

et al. Subjects will be asked to show the route from his or her bedroom to Location 1: from the Location 1 to the Location 2; and from Location 2 to the participant's. Two research assistants will walk with the participant to obtain the following measures:

- 1) Time to move from one location to another/distance. Time will be measured for each of the three routes along with the total distance in (feet/yards) of the path. The average speed of covering this distance will be calculated as  $v = (\text{total distance}) / (\text{total time})$ , thus standardizing variation in distance and the resulting time that could be present among different care communities. If elevators are present, time will be stopped once the participant reaches the elevator and uses it, and time measurement will be resumed upon exiting the elevator. If subjects make a wrong turn, they will be corrected and 2 minutes added for each time they are corrected.
- 2) Errors are defined as the percent of errors made (wrong turns) based on the number of possible turns. Depending upon the route selected by the subject, the number of possible turns is variable so that the percentage of wrong turns will be calculated.

Secondary Outcome: Life Space. Life space is defined as the spatial extent of mobility within an environment, and varies from a small life space (limited to one's room) to a large life space (travels outside of the care community). Life space will be measured using a modified version of Tinetti's Nursing Home Life-Space Diameter at times 0, 1, 3, 6, and 12 months. The tool is a survey that asks subjects or their caregivers to state how often per day (in the past 2 weeks) an individual moves within spaces, including their own rooms, outside the room but within the unit/hallway/floor, outside the unit/hallway/floor but within the care community, and outside the care community. Frequency is rated on a scale from 0 = never to 5 (> 3 times/day) for each level of life space. Scores for each life space are summed, with the total ranging from 0-50 and higher scores representing more mobility and a larger life space. Tinetti reported test-retest reliability of the measure with  $r=.922-951$  using different nurse raters.

A weakness of Tinetti's tool is the reliance on self-report; thus we will use an electronic tracking device to measure life space on a subsample of subjects for one community from each of the arms for years 2-4 of the study (one community for each Arm; Y2 = Arm 1; Y3=Arm2; and Y4 = Arm 3). Tracking devices have been used in healthcare and manufacturing for years, but have only recently been used in long term care. Primarily they have been used to identify when individuals with dementia elope from buildings or areas. Except for one small study involving hard wired monitoring devices, mobility tracking has not been used to measure life space. There is at least one system available that provides a wearable technology (wristband) and "anchors", which are devices that plug into the community's wall outlets. The system uses Bluetooth to identify the participant's location inside to a location to accuracy within 10 feet. The system provides real time tracking and reporting which can be used to track life space. Secure data is stored in the cloud. Because this technology is relatively new, we did not want to rely on it solely. But it would give a much more accurate and detailed report of locational information than the Tinetti measure and provide valuable information about the effect of cues on life space.

Procedure for Tracking: The participants will be instructed to go about their activities as normal. The tracking devices will be placed on the individuals and data will be collected for one week at baseline (prior to interventions); and for one week at each measurement time. For Arm 3 subjects, monitoring will be ceased during the spaced retrieval training time periods. The wristbands can be worn 24 hours/day (they are waterproof), so the participants will be asked to leave the devices on for each week. Study staff will monitor the use of the trackers daily during data collection. If a band is lost, it will be

replaced. Using the tracking device analytics, we will measure the life space of the participants within the community using the zones described in Tinetti's Nursing Home Life-Space Diameter. In addition, we will measure the time spent at each life space zone.

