## 6. Purpose of Research

The overall goal of this project is to assess the contribution of cues and spaced retrieval education on wayfinding ability and life space in persons with wayfinding impairment who live in long term care communities in a randomized controlled trial. We will select nine senior assisted living residences and recruit 137 residents identified as having wayfinding problems who can move themselves and communicate. We will randomize the facilities to one of three arms 1) Control (no changes); 2) Cued (salient environmental landmarks and signage placed at key decision points) plus staff training on use of the cues and 3) Cued plus Spaced- Retrieval education. Subject characteristics including mobility, demographic variables, activities of daily living, and cognitive ability will be measured along with life space mobility (spatial extent of mobility). We will test all subjects' wayfinding ability (primary outcome) and life space (secondary outcome) at baseline and at 1, 3, 6, and 12, months. We will compare wayfinding performance over time among the 3 trial arms.

The specific aims are:

Aim 1: To examine the effect of salient cues with and without spaced retrieval education on wayfinding ability initially and over time in older adults who have wayfinding deficits in long term care communities. HO1: Subjects will have improved wayfinding (faster, more accurate) in the cued condition versus the control condition at months 1, 3, 6, and 12; and post intervention compared to pre intervention.

H02: Subjects in the cued condition + Spaced Retrieval education will have improved wayfinding ability compared to the control and cue alone condition at times 1, 3, 6, and 12 months.

Aim 2: To determine the effects of salient visual cues and spaced retrieval training on life space.

H03: Subjects in the cued conditions will have larger life spaces than those in the control condition at times 1,3, 6 and 12 months.

H04: Wayfinding ability will be positively correlated with larger life space over time.

Exploratory Aim 3: To determine which subject characteristics are most amenable to the intervention; and which subject characteristics place persons at risk for less responsiveness to the intervention so that the intervention can be appropriately targeted.

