**Specific Aim 1** examines the effect of salient cues with and without spaced retrieval education on wayfinding ability. The statistical model #1 for the repeated measures of wayfinding ability at 1, 3, 6, and 12 months will include the following explanatory variables: wayfinding ability at baseline, time (with levels 1, 3, 6, 12 months), trial arm, and control variables measured at baseline (see the measures section). Time will be included as categorical variable with the above mentioned levels to model potentially non-linear (polygonal) changes in outcomes over time. For the first measure of wayfinding ability, average speed calculated as described in the measures section, this model will be implemented as a linear mixed effects (LME). It will also include random effect indicating facility as will all other statistical models. The LME model generalizes classical analysis of repeated measures and allows for data missing at random, time-varying covariates, and structured covariance matrix. The participants who completed at least one post-baseline assessment will be included in the analysis following the intent to treat principle. The second measure of wayfinding ability, the proportion of wrong turns, by definition takes values from the [0, 1] interval and will be analyzed using generalized LME with beta distributed errors. Beta distribution supported on [0, 1] interval is particularly suitable to this measure.

The essential parameter of interest in the statistical model #1 is associated with the trial arm variable. The least square (LS) means corresponding to this variable will be output from the model, and differences among them will be tested. The test of significance of the differences between LS means for cues versus control and cues + spaced retrieval education versus control will yield the formal test of hypothesis H01. The test of the significance of the differences between cues + spaced retrieval education versus cues alone will yield the formal test of hypothesis H02. After testing the main trial arm effects, time by trial arm interaction will be added to the statistical models to explore whether intervention effects change as time progresses. The significance of the interaction term will be assessed, and differences in LS means by trial arm at each time point will be tested to determine the immediate and sustained effects.

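### The speed outcome adds two minutes per corrected wrong turn, so an effect on it cannot by itself be read as faster wayfinding

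*Protocol*

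**What the plan says.** Protocol section 8d, Study Outcomes, defines two wayfinding measures.

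- **Speed.** "The average speed of covering this distance will be calculated as" total distance over total time. The stated purpose is comparability: "thus standardizing variation in distance and the resulting time that could be present among different care communities". The same item then sets the penalty: "If subjects make a wrong turn, they will be corrected and 2 minutes added for each time they are corrected".
- **Errors.** "Errors are defined as the percent of errors made (wrong turns) based on the number of possible turns".

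Amendment #8097 to section 8d changes the start and end points of the routes and leaves the penalty alone.

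H01 in protocol section 6 names both qualities: "Subjects will have improved wayfinding (faster, more accurate) in the cued condition versus the control condition".

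The SAP, under Specific Aim 1, models each measure separately. For speed: "For the first measure of wayfinding ability, average speed calculated as described in the measures section, this model will be implemented as a linear mixed" (an LME, in the SAP's abbreviation). For errors: "the proportion of wrong turns, by definition takes values from the [0, 1] interval and will be analyzed using generalized LME with beta distributed errors". The repeated-measures model "will include the following explanatory variables: wayfinding ability at baseline, time (with levels 1, 3, 6, 12 months), trial arm" and baseline control variables, with a random effect for facility. The SAP plans no version of speed without the penalty and no sensitivity analysis that removes it.

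**The concern.** Because the penalty sits inside the time that defines speed, each corrected wrong turn counts twice: once in the error percentage and once as 120 seconds in speed. If the cues cut wrong turns and leave pace unchanged, recorded speed still rises. A reader of H01 would take a significant speed result as evidence for *faster*, separate from the accuracy result, when it may be the accuracy result seen again. The reverse can also happen: noise from the penalty can hide a real gain in pace.

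The penalty also works against the stated reason for using speed. A constant number of seconds does not scale with distance, so one error costs a larger share of speed on a short course than on a long one. Routes are chosen separately in each community, and communities are the units randomised.

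**Working it through.** **Inputs from the documents.** The penalty is 120 s per correction. Speed is total distance over total time. The planning effect is a reduction of 8 minutes with an SD of 19 minutes (protocol section 7a).

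**Assumed inputs.** The documents give no route length, pace, number of turns or error rate. I took a total distance *D* of 200 to 1,500 ft, a penalty-free pace *s* of 1.5 to 3.5 ft/s (2 ft/s as the central value), and mean error rates of 5% to 30%.

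**The plan's own figure.** 8/19 = 0.42, as stated. In penalty units, 8 minutes is 8/2 = 4 corrections and 19 minutes is 19/2 = 9.5. The documents do not say whether the earlier study used the penalty, so this only shows scale.

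**Step 1: formula.** With *k* corrections, recorded speed is v = D / (D/s + 120k). It rises when *k* falls, with *s* fixed. At 600 ft and 2 ft/s:

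- two corrections: 600/(300 + 240) = 1.11 ft/s
- one correction: 600/(300 + 120) = 1.43 ft/s

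That is a 29% gain in recorded speed with no change of pace.

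**Step 2: cost of one correction.** The proportional loss is 1 − (D/s)/(D/s + 120). At 2 ft/s:

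| Total distance | D/s | Loss |
|---|---|---|
| 300 ft | 150 s | 1 − 150/270 = 44% |
| 600 ft | 300 s | 1 − 300/420 = 29% |
| 1,500 ft | 750 s | 1 − 750/870 = 14% |

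Over the full assumed ranges of distance and pace, the loss runs from 11% to 68%.

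**Step 3: is distance standardised?** At 2 ft/s with two corrections, v = D/(D/2 + 240). This gives 0.77, 1.11, 1.30 and 1.43 ft/s at 300, 600, 900 and 1,200 ft. If corrections instead rise in proportion to distance, at one per 300 ft, then v = D/(D/2 + 0.4D) = 1/0.9 = 1.11 ft/s at every distance. Standardisation holds in the second case and fails in the first.

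**Step 4: share of variance due to errors.** Two simulations were used. Both had mean pace 2 ft/s, SD 0.5 ft/s, and errors independent of pace.

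- *Error percentage as a linear predictor* (beta-distributed error propensity, 300 to 1,500 ft): 32–41% at 5% mean errors, 46–54% at 10%, 60–62% at 20%, about 65% at 30%.
- *Each correction count as its own category* (gamma-Poisson counts), at 300, 900 and 1,500 ft: about 83%, 64% and 48% with a mean of two corrections; about 74%, 45% and 28% with a mean of one; about 60%, 28% and 15% with a mean of 0.5. A straight-line fit at a mean of two gives less, about 57%, 54% and 42%.

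**Step 5: effect on a contrast.** In the first simulation, halving errors with pace unchanged moves v by 0.14–0.15 SD at 5% mean errors and by 0.49–0.58 SD at 30%. A true 10% gain in pace, worth 0.38 SD without the penalty, shrinks to 0.26–0.29 SD at 5% errors and 0.11–0.14 SD at 30%.

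**The case against.** The strongest defence is that the target is wayfinding ability, not walking pace. Participants may use walkers, wheelchairs or scooters. Staff correct each wrong turn, which cuts short the time it would have cost. On that view the penalty charges the participant for help received, and penalised speed is a legitimate composite. This stands, and it is the reason to keep the measure. It does not make the composite evidence for *faster* on its own.

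Three stronger readings are tempting, and the documents do not support them.

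- *The trial cannot separate faster from more accurate.* Errors are measured separately and have their own beta model, so accuracy is tested directly. The gap is confined to the speed analysis.
- *Speed is little more than errors restated.* That depends on inputs the documents do not give. With few corrections on a long course, errors explain about 15% of the variance; with more corrections on a short course, about 80%. Inclusion requires wayfinding impairment exhibited at baseline, which makes very low error rates less likely but fixes no rate.
- *Route length biases the arm comparison.* Routes are picked by space syntax, which counts path length and intersections. Each wave is meant to hold communities similar on that score, and baseline wayfinding ability and a facility random effect are in the model. These soften the concern. They do not remove it, because the arm effect on v can still vary with length, but nothing in the documents shows a tilt between arms.

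**Conclusion.** The concern holds in a limited form. As planned, the speed measure mixes travel time with errors, and the SAP has no analysis that separates them. A positive speed result can arise from fewer errors alone and should not be reported as *faster* on that basis. The claim that dividing distance by time standardises for distance is true only if corrections scale with route length.

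That the penalty enters speed and links it to errors follows from the definition and needs no assumption. The size does: a loss of 44% to 14% per correction between 300 and 1,500 ft rests on 2 ft/s, and the 15% to 80% share of variance rests on the assumed paces, distances and error rates. The comparison between arms remains valid as a comparison of a composite; what needs correcting is the interpretation attached to it.

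**What to change.** 1. Keep the measure, but call it penalised (composite) speed in the protocol, the SAP and reports.
2. Store raw time and number of corrections as separate fields. The protocol does not say that raw time is kept apart from the added minutes. Where it was not, it can be recovered as recorded time minus 2 minutes per correction, provided the count was kept.
3. Prespecify in the SAP the same linear mixed model for unpenalised speed (total distance over observed time without the added minutes) as a supportive analysis.
4. State in advance that an effect on penalised speed alone will be reported as better wayfinding performance, not as *faster*.

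I would not add route distance as a main-effect covariate. It does not address an arm effect that varies with length. If the distance actually walked were used, it would also adjust for something measured after randomisation.

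The cost is one extra model, with no new measurements if times and correction counts are on file. The drawback is that unpenalised speed does not charge the participant for staff correction, so it should be read beside the penalised measure and the error measure, not in place of them.

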8. Wayfinding performance (primary outcome) will be compared between the participants in the care communities repeatedly over a period of 12 months (baseline, 1, 3, 6 and 12 months). The rationale for the time frame of outcome measures is to determine the effects of the interventions initially and over time. This information will be essential to understanding the timing and dosage of the interventions. Most studies that examine wayfinding only look at initial learning or short term retention; we seek to address this problem by assessing the impact of the intervention over a sustained period of time. Subjects will have their life space (secondary outcome) measured via a questionnaire. In addition, one community from each arm (for a total of three communities) will have life space measured via a mobility tracking device at these time frames.

9. Randomization will occur in the same manner in Waves 2-4 with enrollment of residents from nine additional care communities (three in each Wave). Each Wave will have similar communities in terms of space syntax and level of care. Randomization in this manner, a control comparison group, and careful measurement of the complexity of the communities and the subjects' baseline characteristics will provide a rigorous and reproducible study.

Description of ARMS. ARM 1 is the control condition, in which there will be no modifications to décor or signage in the existing care community, and no education on wayfinding. However, subjects will receive the same testing that is provided for the other arms at the designated time periods. ARM 2 consists of adding cues to the environment along the routes being measured for wayfinding. The cues will be comprised of pictures, objects, and signage (described below). The care community staff, residents, and visitors will be given a brochure indicating the purpose for the cues and suggesting ways in which individuals can use the cues for wayfinding. ARM 3 is the cues + spaced retrieval education. This condition will have cues as in ARM 2 added to the care communities. In addition, a spaced retrieval (SR) memory intervention strategy will be implemented individually for each resident participating in the study to help them remember the presence and function of the environmental wayfinding cues.

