### **IRB AMENDMENT TO 8D #9732 - 5/3/2021**

Location tracking will be done by having the subjects wear a "fit bit" type of bracelet for one week at each data collection time frame. Subjects will be instructed to keep the bracelet on for the entire week. A data collector will assist the resident in applying the bracelet if necessary. At the end of the week, the bracelet will be collected, placed in a plastic bag, and locked in the research office. Subjects will wear the same bracelet (it is associated with their subject ID). The data is transmitted, de-identified, to a server placed in the facilities. The server can be dialed into by the researcher, who can monitor if there is no activity by the subject and intervene if necessary. The use of the tracking device is already in the current informed consent document. The subject will be given instructions about caring for the device (they can bathe with it on, they should wear it all the time, etc.) and we will check with them daily to make sure everything is going OK. Like all parts of our study, they can refuse this at any time.

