#### **IRB AMENDMENT TO 8D. #8097 - 2/22/2019**

##### **1) Addition of data collection timeline to study step #8**

"Wayfinding performance (primary outcome) will be compared between the participants in the care communities repeatedly over a period of 12 months (baseline, 1, 3, 6 and 12 months). Subjects may be scheduled two weeks after or two weeks before the exact 1, 3, 6, and 12-month date to accommodate for scheduling conflicts. The rationale for the time frame of outcome measures is to determine the effects of the interventions initially and over time. This information will be essential to understanding the timing and dosage of the interventions. Most studies that examine wayfinding only look at initial learning or short-term retention; we seek to address this problem by assessing the impact of the intervention over a sustained period of time. Subjects will have their life space (secondary outcome) measured via a questionnaire. In addition, one community from each arm (for a total of three communities) will have Life space measured via a mobility tracking device at these time frames."

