## Statistical Analysis Plan

**Management and Analysis.** The data will be entered into the study database, cleaned and assessed for completeness. Then the data will be de-identified and transferred into SAS 9.4 statistical software for analysis.

**Preliminary analysis.** The distributions of outcomes and control variables will be summarized. For continuous outcomes, normalizing transformations will be applied as needed. If they are not successful, then the modeling approach will involve generalized linear models with the appropriate error distribution (e.g., gamma or beta). Since the level of randomization is facility and the unit of analysis is individual, the appropriate random effects will be specified in all statistical models to account for nesting of individuals within facilities.

**Analysis of feasibility measures.** Attrition rates and reasons and baseline measures of the dropouts will be compared by trial arm to ensure absence of attrition bias. Resident responses to the acceptance of cues questionnaire and staff responses to the interview questions will be summarized overall, by trial arm (cues only versus cues + spaced retrieval education), and by care community. The staff focus group data will be transcribed into *Atlas Ti* and analyzed using constant comparison analysis. Text will be chunked into common units and assigned a code. Codes will be grouped into like categories (axial coding) and then like categories will be assigned themes. Similarities and differences of themes among the arms and care communities will be summarized.

**Primary analysis.** The primary analysis will follow the intent to treat approach and will include all participants as randomized.

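### Tracked life space comes from one community per arm, each arm in a different study year, so an arm comparison of these data cannot show an effect of cues

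*Protocol*

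**What the plan says.** Protocol section 8d, under Secondary Outcome: Life Space, adds an electronic tracker because the life-space questionnaire depends on self-report. The tracker goes to a subsample in study years 2 to 4, allocated as "one community for each Arm; Y2 = Arm 1; Y3=Arm2; and Y4 = Arm 3". The same paragraph expects the device to be more accurate and detailed than the questionnaire and to "provide valuable information about the effect of cues on life space".

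Study step 8 of section 8d gives the same count: "one community from each arm (for a total of three communities) will have life space measured via a mobility tracking device". The 2019 amendment to 8D (#8097) repeats it. Neither place mentions staggered years. The 2021 amendment to 8D (#9732) describes the bracelet and has it worn "for one week at each data collection time frame", but names no communities, arms or years, so it leaves the allocation as it was.

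Under Procedure for Tracking, "data will be collected for one week at baseline (prior to interventions); and for one week at each measurement time". A tracked baseline is therefore planned.

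The SAP recognises the clustering ("Since the level of randomization is facility and the unit of analysis is individual") and says of the mixed model for Aim 1: "It will also include random effect indicating facility as will all other statistical models". For Aim 2 it says that life space will be analysed first with the questionnaire in all participants. No tracker analysis follows, and no caveat about one.

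**The concern.** Facilities are randomised. An arm effect must therefore be judged against the variation between facilities in the same arm, and one tracked facility per arm shows no such variation. Placing Arms 1, 2 and 3 in different study years ties arm to calendar time as well.

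Calendar time is not neutral in this trial. Section 10 records that data collection and recruitment were halted in 2020, and a later amendment there (#10128) describes sites closing for 10 days at a time. Amendment #9338 to 8D reports six communities closed out, because of visitor restrictions and because their study year had ended. Such conditions could plausibly change how far residents move, which is what the tracker measures.

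The stake is limited but real. A difference in tracked life space between the three communities could be reported as an effect of cues when the building's history or the year explains it equally well.

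**Working it through.** **1. The plan's own figures.** The protocol gives no size, power or intraclass correlation (ICC) for the tracked subsample. The nearest figures are in section 7a, where the sample is sized for wayfinding: 137 participants, about 11 per community, ICC 0.0012. They are consistent with each other: 137/12 = 11.4, and the stated design effect is reproduced by 1 + (36 − 1) × 0.0012 = 1.042. For a community of 11 it would be 1 + 10 × 0.0012 = 1.012.

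**2. Aliasing.** Take the schedule as written, with an intercept and two indicator columns each for arm, community and year: 1 + 2 + 2 + 2 = 7 columns. Each community has one arm and one year, so the three sets of indicators are identical and the matrix has rank 3. Arm, community and year cannot be told apart.

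**3. Degrees of freedom for community within arm** (communities minus arms):
- tracked subsample: 3 − 3 = 0
- all 12 communities of section 8d: 12 − 3 = 9

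**4. What the baseline week changes.** Write the change from baseline in the Arm 2 community as β + g(Y3) + e(2), and in the Arm 1 community as g(Y2) + e(1). Here β is the cue effect, g the change due to calendar time, and e the change due to events at that site. A stable difference in level between the two buildings cancels. The difference in change is

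β + [g(Y3) − g(Y2)] + [e(2) − e(1)].

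This is one observed contrast containing three unknown parts. If tracking were concurrent, the g terms would be equal only so far as calendar effects were common to the sites, and the e terms would remain.

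**5. The SAP's facility effect.** With m residents per community, the variance of an arm contrast is 2 × (between-facility variance + within-facility variance/m). With one facility per arm, nothing in the data estimates the between-facility part separately from the arm difference. The required model therefore yields no valid arm test.

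**6. Illustration only: facility ignored, contrary to the SAP.** Two communities of 11 are compared by t-test with 20 df and critical value 2.086. The ratio of true to estimated variance is r = (1 + 10 × ICC)/(1 − ICC), and the false positive rate is 2 × P(t > 2.086/√r). Only the first ICC is from the protocol.

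| ICC | False positive rate |
|---|---|
| 0.0012 (protocol, for wayfinding) | 5.1% |
| 0.01 (assumed) | 6.2% |
| 0.05 (assumed) | 11.3% |
| 0.10 (assumed) | 17.7% |
| 0.20 (assumed) | 29.4% |

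A small ICC does not protect against a systematic shift tied to site or year. At ICC 0.0012, √r = √(1.012/0.9988) = 1.0066. A shift of d SD with no cue effect gives non-centrality d × √(11/2)/1.0066. The test then declares an arm effect 8.8% of the time for d = 0.25, 20.2% for d = 0.5 and 60.6% for d = 1.0. These shifts are assumed; the documents give none.

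**The case against.** The strongest defence is that no hypothesis, test or power statement concerns the tracker. The questionnaire comes first in the SAP. The protocol declines to depend on the new technology alone, and it maps the tracked zones to those of the questionnaire, which is already close to a validation role. The baseline week removes stable building differences. Change within the Arm 2 and Arm 3 communities, though uncontrolled, is still some information. The staggered years appear in one paragraph only, and the trial describes itself as a pilot.

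Most of this stands and narrows the point. It does not remove it: the effect-of-cues sentence is current text, no later amendment withdraws it or the schedule, and the SAP adds no limit. If the staggering were dropped, arm and community would still coincide.

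A reader might infer more than the documents support:
- *That the life-space comparison as a whole fails.* H03 is tested on the questionnaire in all participants and does not use the tracked subsample.
- *That the plan contains a test with an inflated error rate of, say, 10% to 20%.* Such rates need participants treated as independent, which the SAP rules out, and ICCs far above 0.0012. At 0.0012 the rate is about 5.1%.
- *That any arm difference could simply reflect the building.* Baseline adjustment deals with stable differences in level; site-specific change and calendar time remain.
- *That tracker results would displace the questionnaire.* Nothing in the text says so, and the protocol's caution about the technology points the other way.
- *That the pandemic distorted a particular arm.* The documents do not date study years 2 to 4, so the overlap is unknown.

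**Conclusion.** The point holds for the tracker subsample. As scheduled, arm is completely aliased with community (0 df for community within arm) and with study year. The baseline week repairs only stable differences in level. An arm comparison of tracked life space cannot therefore deliver the information on cues that the protocol expects from it.

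This follows from the allocation itself and needs no assumed ICC or shift; the percentages in the working are illustrations. The year part rests on the Y2, Y3, Y4 schedule being in force, whereas the community part does not. No primary analysis and no test of H03 changes. The plan should be corrected, but the correction concerns what may be claimed from a supplementary measure.

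**What to change.** State in the protocol and the SAP that tracker data have two uses:
- **Validation of the questionnaire:** the association of tracked zones and time in each zone with the questionnaire score, pooled over the three communities and five time points, and allowing for repeated measures and for community.
- **Description:** change from baseline within each community.

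Add that no between-arm test or claim will be made from these data, and qualify or delete the effect-of-cues sentence in section 8d. This costs only wording; the trial gives up a comparison that it cannot support.

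Optionally, where equipment allows, track the three communities of one wave together. Study steps 5 and 9 imply, without saying so outright, that each wave holds one community per arm. This removes the year alias but leaves arm and community identical, so the wording change is needed in any case. Its cost is more bands in use at one time.
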